Cover page

Official title:

Modelling propofol pharmacokinetics and pharmacodynamics during an intravenous anaesthesia guided by the bispectral index (BIS)

NCT number:

NCT02713698

Date of the document:

08/01/2016

Study protocol and statistical analysis plan

Anaesthetic protocol

Preoperative evaluation

- Assessment of past medical history, allergies and current medications;
- Physical exam (vital signals, weight, height) and airway assessment with Mallampati score, dentition, range of neck motion and thyromental distance;
- Laboratory tests confirmation when necessary;
- Frailty quantitative clinical evaluation Clinical Frailty Scale;
- Single-frequency bioelectrical impedance analysis;
- Presentation and discussion of informed consent elements;
- Participant information leaflet delivery.

Anaesthetic technique

- Intra-operative monitoring: continuous pulse oximetry, electrocardiography, invasive blood pressure, neuromuscular blockade (*train-of-four* pattern) and bilateral BIS (BIS VISTATM Bilateral Monitoring System, Covidien, Colorado, US);
- Remifentanil effect-site concentration set at 3 ng/mL (Minto's model), using a target controlled infusion device (Orchestra® Base Primea – Fresenius Kabi) and arterial line placement;
- Induction of general anaesthesia: remifentanil effect-site concentration set at 3 ng/mL, rocuronium 0.6 mg/kg and propofol at 2000 mg/h until LOC, defined by "loss of eyelash reflex" and "loss of response to name calling";
- At LOC, propofol infusion rate will be adjusted to 6 mL/kg/h and orotracheal intubation will be accomplished when TOF count 0-1 and BIS 40-60;
- Time to LOC in seconds and total dose of propofol in mg will be recorded;
- Maintenance of general anaesthesia: remifentanil effect-site target will be adjusted by 0,5 ng/mL changes according to physiologic parameters, propofol will be altered by 5 mg/mL changes targeting the BIS values between 40 and 60 and rocuronium 0.1 mg/kg in order to maintain TOF count ≤ 2;

- Maintenance fluid requirements follow estimated by the 4-2-1 rule: 4 mL/kg/h for the first 10 kg, 2 mL/kg/h for the second 10 kg and 1 mL/kg/h for every kg above 20 kg;
- Parameters of mechanical ventilation: volume-controlled mode, tidal volume 6-8
 mL/kg, PEEP (positive end-expiratory pressure) 5 mmHg and FiO₂ 40-50%;
- Thirty min before the end of surgery intravenous paracetamol 1000 mg, parecoxibe 40 mg and tramadol 100 mg will be administered;
- Postoperative nausea and vomiting prophylaxis with dexamethasone 4 mg in the beginning of surgery and ondansetron 4 mg thirty min before the end of surgery;
- At the end of surgery, propofol and remifentanil infusions will be discontinued and neostigmine 2.5 mg and atropine 1 mg or sugammadex 2 mg/kg will be administered to reversal neuromuscular blockade;
- Extubation will be performed after an adequate reversal of neuromuscular blockade (TOF ratio ≥ 90%) considering consciousness recovery and respiratory mechanics adequacy;
- Arterial blood samples will be obtained after arterial line placement, immediately
 after LOC, immediately before surgery and after every 20-30 min during propofol
 infusion. After stopping propofol infusion, arterial blood samples will be acquired
 every 10 min until recovery of consciousness. The maximum blood sample per patient
 will be 20 mL;
- Total dose of propofol and total dose of remifentanil, total time of propofol and remifentanil infusion and the time until consciousness recovery after propofol discontinuation will be recorded.

Post-operative evaluation

 Application of modified Brice protocol in the recovery room and in the first 24-48 h after the surgery.

*With respect to patients submitted to an orthopaedic surgery, the anaesthetic protocol will be slightly different considering the standard practice in the hospital. When indicated, a peripheral nerve block will be executed and the opioid of choice will be fentanyl instead of remifentanil. When possible, a laryngeal mask airway will be used.

Quantification of serum propofol concentration

The quantification of propofol in plasma will be performed using gas chromatography/ion trap-mass spectrometry (GC/IT-MS).

Arterial blood samples are collected into serum tubes and centrifuged at 4000 rpm for 5 min in order to obtain plasma. Serum is preserved at -80 °C until analysis.

Extraction procedure is performed by the addition of 50 μ L of thymol (0.01 mg/mL) and 1mL of ultra-pure water to a 0.5 mL aliquot of serum and to the propofol calibration standards. To each processed sample 0.5 mL of burate buffer (pH=9) is added and mixed by inversion for 5 min. Then, 300 μ L of chloroform:ethylacetate (70:30 v:v) is added and also mixed by inversion for 20 min. After a 10 min centrifugation, 2 μ L of the organic phase is injected into the GC/IT-MS injector.

The identification of propofol in each sample is performed in the same chromatographic conditions, by comparative analysis between the retention times of pure compounds with the compounds in the injected samples. Blank samples are obtained from propofol-free plasma, which were requested to the Clinical Haematology Service of CHP. All the plasma donors received both written and oral information regarding the study and they signed informed consent.

Statistical analysis: PKPD Modeling Analysis

A conventional 3-compartment, first-order elimination, PK model will be used to fit propofol data. Parameter estimates will be obtained using a nonlinear mixed effects model with the program NONMEM.

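### Does the unstated timing of rocuronium relative to loss of consciousness make the recorded LOC time and dose unusable?

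*Combined protocol and SAP*

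**What the plan says.** The induction bullet under Anaesthetic technique puts remifentanil, rocuronium and propofol in one step: "rocuronium 0.6 mg/kg and propofol at 2000 mg/h until LOC, defined by" two signs, the second being "loss of response to name calling". The limit attaches to the propofol infusion. Nothing says whether rocuronium comes before or after LOC is judged.

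The monitoring bullet includes "neuromuscular blockade (*train-of-four* pattern) and bilateral BIS". Neither measure is part of the LOC definition. They first appear as conditions for intubation, which comes after LOC.

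LOC has three consequences:

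- It changes the infusion: "At LOC, propofol infusion rate will be adjusted to" a new value.
- It is recorded: "Time to LOC in seconds and total dose of propofol in mg will be recorded".
- It times one arterial sample, drawn immediately "after LOC, immediately before surgery and after every 20-30 min during propofol" infusion.

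For orthopaedic patients "the anaesthetic protocol will be slightly different considering the standard practice in the hospital". The differences named are a nerve block, fentanyl in place of remifentanil, and a laryngeal mask. Rocuronium is not mentioned.

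The only model described under Statistical analysis is pharmacokinetic: "A conventional 3-compartment, first-order elimination, PK model will be used to fit propofol data".

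**The concern.** A patient who is still conscious but weakened by developing block may fail to blink or answer. If rocuronium is already acting when the signs are tested, LOC could be called before propofol alone would have produced it. Recorded time to LOC would then be too short and the dose at LOC too small, and the sample taken just after LOC would be misread by anyone treating it as the concentration at LOC.

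The dose offers no cross-check. The rate is constant until LOC, so dose is simply rate times time and carries the same error. The plan asks for neither the rocuronium time nor a train-of-four (TOF) reading at LOC, so an analyst could not reliably tell affected patients from unaffected ones. The title and the analysis heading both promise pharmacodynamic as well as pharmacokinetic modelling, so LOC values might later be used as effect data.

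**Working it through.** The plan states no figure on this point, so there is nothing to reproduce. Four checks matter.

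**1. Does the text fix the order?** No. The induction bullet lists the drugs together, and the next bullet does not include giving rocuronium among the actions at LOC. The TOF and BIS conditions for intubation fit either order. This is silence. No two statements conflict.

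**2. When would block cause an early call?** LOC needs both signs to be lost. Let propofol alone abolish the signs at times a and b, with a < b, so true LOC is at T = b. Let block alone abolish them at a′ and b′. Treating the two effects as separate, LOC is observed at max{min(a, a′), min(b, b′)}. This is earlier than b only if b′ < b, that is, if block removes the later sign before propofol does. If block has not already taken the first sign (a′ ≥ a), the error is b − max(a, b′), which cannot exceed b − a. Losing one sign to block does not trigger LOC while the other persists.

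Signs tested at intervals are also noticed at or after their true loss. With detection delay d ≥ 0 and block error e ≥ 0, the net error is d − e. Only the block component is bound to run early.

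**3. How large could it be?** The one documented input is the induction rate: 2000 mg/h ÷ 3600 s/h = 0.556 mg/s.

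- Dose at LOC = 0.556 × T.
- Shortfall = 0.556 × e.
- Relative error = (0.556 × e) ÷ (0.556 × T) = e/T, for time and dose alike.

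The documents give neither T nor e, nor an onset time for rocuronium. With assumed values:

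| Assumed T | Dose at T | e = 0 | e = 10 s (5.6 mg) | e = 30 s (16.7 mg) |
|---|---|---|---|---|
| 60 s | 33.3 mg | 0% | 16.7% | 50.0% |
| 120 s | 66.7 mg | 0% | 8.3% | 25.0% |
| 180 s | 100.0 mg | 0% | 5.6% | 16.7% |

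The 50% cell pairs the longest assumed error with the shortest assumed time and deserves no weight. The dose column also assumes that the total dose recorded in the induction steps means dose at LOC. That is a fair reading, because an overall total is listed separately later, but the wording does not say so.

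**4. What does the error reach?** If LOC is called at T − e, the rate change and the sample also happen early. The dose actually given by then is 0.556 × (T − e), and the measured concentration belongs to that dosing history. A compartmental fit to actual infusion and sampling times therefore takes in correct data. Only the label LOC is wrong, and no described analysis uses that label.

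**The case for a change.** The strongest case for acting is that the omission is cheap to repair now and may be impossible to repair later. The study announces pharmacodynamic modelling, takes the trouble to record LOC in seconds, and ties a blood sample to it. One sentence on order, one recorded time and one TOF reading would let later users separate clean values from doubtful ones. Any error might also differ between orthopaedic and other patients if relaxant use differs.

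Part of this stands. The order is unstated, the direction of the block component is right, and whether the rocuronium step applies to orthopaedic patients is open.

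The rest yields little. A rocuronium time would classify patients but would not give e, so no value could be corrected. If practice is uniform, every patient given rocuronium falls in one class. The obvious analytic remedy is to treat LOC called after rocuronium as known only to lie beyond the last test with a response. If rocuronium routinely comes first, nearly every such value becomes a lower bound with no upper bound, and a median could not be estimated without outside assumptions. If rocuronium always follows LOC, the rule does nothing. It helps only under mixed practice, which the documents do not show. It would also need repeated, time-stamped testing and a TOF monitor running at LOC, and neither is described. No comparison between surgical groups is planned.

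**Conclusion.** No change to the plan is called for. The omission is a missing detail at induction, and no estimate the plan commits to depends on it. The error is zero if rocuronium follows LOC. Otherwise its size cannot be derived from the documents. Its form is e/T for both time and dose, at 0.556 mg per second of early calling, and it is offset to an unknown degree by delay in noticing the loss of the signs.

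This rests on three assumptions: the pharmacokinetic fit uses actual infusion and sampling times; LOC time, LOC dose and the sample just after LOC are not used as pharmacodynamic endpoints; and BIS, which the title and the maintenance target point to, is the measure of effect. If LOC values were later analysed as effect data, that report should say whether rocuronium had been given before LOC was judged. That is a caution for such an analysis and leaves this plan as it is. Nothing here bears on which order of drugs is clinically right.

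### Two propofol dosing instructions have unusable units: the maintenance step is a concentration applied to an infusion rate, and the post-LOC rate is a volume with no stated emulsion strength

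*Combined protocol and SAP*

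**What the plan says.** All the propofol dosing text is in the Anaesthetic technique section, under Anaesthetic protocol.

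- Induction is a mass rate: "propofol at 2000 mg/h until LOC".
- The next bullet changes to a volume rate per kilogram: "At LOC, propofol infusion rate will be adjusted to 6 mL/kg/h".
- The maintenance bullet gives the titration step: "propofol will be altered by 5 mg/mL changes targeting the BIS values between 40 and 60".

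For remifentanil the plan does describe a concentration-based scheme: "Remifentanil effect-site concentration set at 3 ng/mL (Minto's model), using a target controlled infusion device". Its maintenance step is in matching units: "remifentanil effect-site target will be adjusted by 0,5 ng/mL changes according to physiologic parameters". No device, model or target concentration is given for propofol.

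The only other infusion expressed in mL/kg/h is maintenance fluid: "4 mL/kg/h for the first 10 kg, 2 mL/kg/h for the second 10 kg and 1 mL/kg/h for every kg above 20 kg".

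The strength of the propofol emulsion is not stated anywhere. The note on orthopaedic patients changes other parts of the technique ("a peripheral nerve block will be executed and the opioid of choice will be fentanyl instead of remifentanil", and a laryngeal mask where possible) but gives no other propofol rate, so it corrects neither bullet.

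**The concern.** Propofol is the studied drug, and these two bullets govern its dosing from LOC until the infusion stops.

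The first fault is dimensional. Mass per volume cannot be added to or subtracted from a rate in mg/h, mg/kg/h or mL/kg/h. Each anaesthetist has to choose a titration step, and a later reader cannot reproduce the one used.

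The second fault is that the rate from LOC onward defines no dose in mg. A volume rate is not invalid in itself, but without a stated strength the same instruction gives different doses with different emulsions. Depending on strength and weight, the literal reading could raise the rate just after LOC.

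What is at stake is safe and reproducible dosing. No claim is made that the pharmacokinetic fit would be biased.

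**Working it through.** The plan states no figure to reproduce here, so the check is one of units and then of arithmetic.

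**Inputs from the document:** induction 2000 mg/h; post-LOC rate 6 mL/kg/h; maintenance step 5 mg/mL; remifentanil step 0.5 ng/mL; the 4-2-1 fluid rule. **Assumptions not in the document:** body weights of 50, 70 and 100 kg; emulsion strengths of 5, 10 and 20 mg/mL.

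**1. The maintenance step.** The quantity being altered is a rate (mass/time or volume/time), and the step is mass/volume, so the dimensions do not match. Treating it as a target-concentration step does not help. No propofol target or model is given, and 5 mg/mL = 5,000,000 ng/mL, which is 5,000,000 / 0.5 = 10 million times the remifentanil step in the same bullet. No size is calculated for this fault because the intended unit is unknown.

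**2. The post-LOC rate against the fluid rule (no strength needed).** For weight W above 20 kg, the fluid rule gives 10×4 + 10×2 + (W − 20)×1 = W + 40 mL/h. The literal propofol volume is 6W mL/h, so the ratio is 6W/(W + 40). It exceeds 3 when 6W > 3W + 120, that is, above 40 kg.

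**3. The post-LOC rate against induction.** The literal rate equals 2000 mg/h at a strength of 2000/(6W) mg/mL. Read instead as 6 mg/kg/h, it is 6W mg/h.

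| | 50 kg | 70 kg | 100 kg |
|---|---|---|---|
| Literal volume, 6W (mL/h) | 300 | 420 | 600 |
| Fluid rule, W + 40 (mL/h) | 90 | 110 | 140 |
| Ratio | 3.3 | 3.8 | 4.3 |
| Break-even strength, 2000/(6W) (mg/mL) | 6.7 | 4.8 | 3.3 |
| If 6 mg/kg/h (mg/h) | 300 | 420 | 600 |
| As a share of 2000 mg/h | 15% | 21% | 30% |

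**4. Literal rate at 70 kg, by assumed strength.**

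- 5 mg/mL: 420 × 5 = 2,100 mg/h, 1.05 times induction. At this strength the break-even weight is 2000/(6 × 5) = 66.7 kg, and a lighter patient would step down.
- 10 mg/mL: 420 × 10 = 4,200 mg/h, 2.1 times induction.
- 20 mg/mL: 420 × 20 = 8,400 mg/h, 4.2 times induction.

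**The case against.** The dimensional fault in the maintenance step is hard to contest. The stronger objections concern the post-LOC rate and the weight given to the whole point.

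- **The mg/kg/h reading is an inference.** The bullet says the rate is adjusted, not reduced, so arguing from a step down presumes the direction. Nothing in the plan ties propofol volume to the fluid rule, and that ratio exceeds 3 only above 40 kg, while the document sets no weight limits. The rise after LOC also depends on an unstated strength. All of this is correct. What remains is that the document cannot be converted to a mass dose and that the literal volume is implausible for typical adults.
- **A clinician holding the vial can convert.** This is true, and because the dose to LOC is recorded in mg, some conversion is evidently expected. The defect is that the document omits the strength. That answers only the post-LOC rate; knowing the strength does not rescue the maintenance step.
- **The consequences are bounded.** Intubation waits for BIS 40-60, maintenance is titrated to the same range under invasive pressure monitoring, and total doses and infusion times are recorded. These safeguards make a sustained overdose less likely. They act after the dose is given, however, and leave the instruction as it stands.
- **The units might be misread from the PDF.** This cannot be fully excluded. Other units in the same section read cleanly, which makes it unlikely.

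**Conclusion.** The concern holds, and the text should be corrected before it is relied on for dosing.

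That the maintenance step is wrong as written is certain, and it rests on no assumption. That the post-LOC rate cannot be turned into a mass dose from the document is also certain. That mg/kg/h was meant is probable but not proven.

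The size of the second fault depends on the reading. At 10 or 20 mg/mL and 70 kg, the literal and inferred rates differ tenfold or twentyfold (4,200 or 8,400 against 420 mg/h). The weights and strengths are illustrative. The conclusion that both bullets need correcting does not depend on them.

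**What to change.** The sponsor's clinicians should:

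1. Confirm the intended post-LOC rate and restate it as a mass rate, probably in mg/kg/h.
2. Restate the maintenance step as a change in rate, in the same unit as the post-LOC rate.
3. State the propofol concentration in use.

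The values are theirs to set; this review proposes none.

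If patients have already been treated, the rates actually delivered should be checked. The plan lists the dose and time to LOC, total doses and total infusion times, but no rate history. From those items, (total dose − dose to LOC) / (total infusion time − time to LOC) gives each patient's average rate after LOC. The rate immediately after LOC would need pump or anaesthetic records, if they were kept.

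The cost is a wording amendment to two bullets, with no extra patients, procedures or samples. The look-back adds work only if treatment has begun.

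### No draw is explicitly specified at recovery of consciousness, so a patient who wakes within 10 minutes of stopping propofol may give no post-infusion concentration

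*Combined protocol and SAP*

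**What the plan says.** All sampling rules are in the combined protocol and SAP, under Anaesthetic technique. The first sample follows arterial line placement. Later ones are taken immediately "after LOC, immediately before surgery and after every 20-30 min during propofol" infusion. For the period after the infusion stops, the rule and the start of the volume limit (20 mL) read "every 10 min until recovery of consciousness. The maximum blood sample per patient".

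The same section defines LOC by two clinical signs and times it: "Time to LOC in seconds and total dose of propofol in mg will be recorded". Recovery is timed as well: "the time until consciousness recovery after propofol discontinuation will be recorded". No signs are given that define recovery, and no sample is named at that moment.

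The statistical section (PKPD Modeling Analysis) states the structural model, "A conventional 3-compartment, first-order elimination, PK model will be used to fit propofol data", and the estimation method, a nonlinear mixed effects model in NONMEM. It describes no pharmacodynamic model, although the official title names pharmacodynamics as a subject of the study.

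**The concern.** LOC and recovery are the two transitions of consciousness in each patient, and the plan treats them differently. LOC has a definition, a time and a concentration. Recovery has a time only.

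If the first post-infusion draw falls 10 min after the stop, a patient who wakes earlier has no measurement after the infusion ends. The concentration at the recorded recovery time is then a model prediction, made across a steep fall in a phase where that patient has no data.

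This matters more because maintenance holds BIS at 40-60, so maintenance samples cover a narrow range of effect, and the first sample appears to precede propofol. In an early waker, the LOC sample would then be the only on-drug concentration outside maintenance. A recovery sample would make it two. A concentration not drawn at waking cannot be obtained later.

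**Working it through.** The plan states no sample size, infusion length, recovery time, volume per draw or parameter values, so it has no figure to reproduce. Everything numerical in steps 2 to 4 is conditional on the assumptions listed.

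**1. The two events side by side**

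| | LOC | Recovery of consciousness |
|---|---|---|
| Operational definition | two clinical signs | none |
| Time recorded | yes | yes |
| Draw tied to the event | yes | not explicitly |

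**2. How many patients could be affected**

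Assume a first draw at 10 min and a lognormal recovery time with median m. Then P(no post-infusion draw) = Φ(ln(10/m)/s), where s = √ln(1+CV²). For CV 30%, s = √ln 1.09 = 0.294; for CV 50%, s = √ln 1.25 = 0.472. Example: m = 8 min and CV 30% give ln(1.25)/0.294 = 0.76, so P = 0.78.

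| Assumed median recovery (min) | CV 30% | CV 50% |
|---|---|---|
| 6 | 96% | 86% |
| 8 | 78% | 68% |
| 10 | 50% | 50% |
| 12 | 27% | 35% |
| 15 | 8% | 20% |

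A range of 8-96% means that the documents cannot settle the share.

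**3. What a recovery draw adds for an early waker**

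Assumed inputs:
- six three-compartment parameter sets: CL 1.5-1.8 L/min, V1 4.5-9 L, Q2 1.4-1.8 L/min, V2 19-32 L, Q3 0.75-1.0 L/min, V3 80-240 L;
- the protocol's induction rate for 2.5 min, then an illustrative varying maintenance rate, with infusions of 60-240 min;
- between-patient SD ω of 30 or 40%, residual error σ of 15 or 20%;
- intra-operative draws every 20, 25 or 30 min, and recovery at 5, 7 or 9 min.

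This gives 6 sets × 5 durations × 3 spacings × 3 recovery times = 270 cases for each ω and σ.

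The variance of the predicted log concentration at recovery is g′(I/ω² + J′J/σ²)⁻¹g. J holds the sensitivities of the sampled log concentrations to the log parameters, and g holds those at recovery. Population parameters are taken as known, which is the best case.

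- Fall in concentration from stop to recovery: 30-72%, median 54%.
- Standard error with no post-infusion draw: 10-32%, medians 17-23%.
- Standard error with a recovery draw: 8-17%, medians 11-15%.
- Median reduction: 29-40%, or 27-39% if the draw replaces one intra-operative draw.

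Hand check: in this linear setting, a measurement at recovery with error σ turns a standard error s₀ into s₀σ/√(s₀²+σ²). Pair the lower values with each other, and likewise the upper:
- medians: 0.17 × 0.15/√(0.0289+0.0225) = 0.11, and 0.23 × 0.20/√(0.0529+0.0400) = 0.15;
- extremes: 0.10 × 0.15/√(0.0100+0.0225) = 0.08, and 0.32 × 0.20/√(0.1024+0.0400) = 0.17.

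These match the ranges above.

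Nonlinear check: 120 simulated patients in each of three cases gave root mean squared errors of 0.201, 0.147 and 0.133 without the draw and 0.123, 0.104 and 0.103 with it. The reductions are 1 − 0.123/0.201 = 39%, 1 − 0.104/0.147 = 29% and 1 − 0.103/0.133 = 23%.

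Later wakers: with similar assumed inputs, the reduction was 30-42% for recovery at 5-9 min and 21-31% at 11-19 min, where a 10-min draw already exists.

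**4. Room within the 20 mL cap**

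The assay uses a 0.5 mL serum aliquot. At an assumed serum yield of 40-50%, that needs 0.5/0.5 = 1 mL to 0.5/0.4 = 1.25 mL of blood, so 20 mL allows 20 to 16 draws. At an assumed 2 mL per draw it allows 10. Three draws are used by the start of surgery. Time covered by interval draws = (draws − 3 − reserved) × 20 or 30 min:
- at 1-1.25 mL, none reserved: 13 × 20 = 260 to 17 × 30 = 510 min; one reserved: 12 × 20 = 240 to 16 × 30 = 480 min;
- at 2 mL, none reserved: 7 × 20 = 140 to 7 × 30 = 210 min; one reserved: 6 × 20 = 120 to 6 × 30 = 180 min.

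Reserving one draw brings the cap forward by one interval.

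**The case against.** The strongest reply is that sampling until recovery may already include a sample at recovery, and that the 10-min clock could start at time zero. A reader might infer that the plan rules out a recovery sample. It does not; the wording is open. On the inclusive reading the change only clarifies the text. It is still useful, because staff could otherwise apply the rule differently between patients. A draw at the moment of stopping would not measure the concentration at waking.

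Second, step 3 concerns pharmacokinetic prediction only. While arterial concentration falls quickly it need not equal the effect-site concentration, so a recovery sample still needs a model before it says anything about effect. BIS is also monitored throughout surgery, so pharmacodynamic information does not rest on LOC and recovery alone. Both points stand.

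Third, a reader might infer that sampling which ends at recovery cannot support the slow compartment, and that the lack of a fallback rule for V3 and Q3 is a defect. The documents do not support that. With an assumed 40 patients, the relative standard error of V3 ranged from 26-47% in the 4 most favourable of 36 assumed scenarios to above 100% in 27. That shows dependence on unstated inputs, not this trial's precision, and above 100% means imprecise rather than unidentifiable. Under similar assumptions the typical concentration within the sampled window was still predicted with a median standard error of 6-7%. A fallback rule is a detail that analysts would ordinarily handle. The recovery draw would not settle the matter either: it lowers the V3 relative standard error by only 11-28%.

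**Conclusion.** The point holds as a small, inexpensive improvement to the sampling rule. The plan pairs LOC with a concentration and does not explicitly do so for recovery. On the plain reading, patients who wake before 10 min contribute nothing after the infusion stops.

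For those who wake at 5-9 min, the median standard error of the predicted concentration at recovery would fall by roughly a third. This rests on assumed pharmacokinetic values, variability and infusion lengths, with population parameters treated as known.

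A reader might go further and infer that the pharmacodynamic aim is compromised, or that most patients are affected. Neither follows. No pharmacodynamic model is described from which a loss could be computed, and no recovery times are given from which a share could be derived.

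**What to change.** In the sampling paragraph under Anaesthetic technique:
- state that one arterial sample is taken at recovery of consciousness whatever the 10-min clock, and that its exact time is recorded;
- reserve its volume within the existing 20 mL cap;
- define recovery operationally for the purpose of timing this sample, for example by the same signs used for LOC, since without a definition the draw cannot be timed consistently.

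The cost is one more draw from a line already in place, a sentence or two of text and, in long cases, possibly one fewer intra-operative draw. Even if the draw replaces an intra-operative one, most of the gain remains (27-39% against 29-40%).

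As a suggestion only, the analysis could also report relative standard errors and shrinkage for the model parameters.

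### Does the mixed use of serum and plasma in the assay section leave the propofol concentrations undefined?

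*Combined protocol and SAP*

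**What the plan says.** The section headed "Quantification of serum propofol concentration" goes on, in its first sentence, to say that propofol will be quantified in plasma. On collection it says "Arterial blood samples are collected into serum tubes and centrifuged at 4000 rpm for 5 min in order to obtain plasma", followed directly by "Serum is preserved at -80 °C until analysis". Extraction adds thymol and 1 mL "of ultra-pure water to a 0.5 mL aliquot of serum and to the propofol calibration standards". The calibration standards appear nowhere else, and nothing is said about the fluid in which they are made up.

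The section closes with identification of propofol, done "by comparative analysis between the retention times of pure compounds with the compounds in the injected samples", and with the blanks: "Blank samples are obtained from propofol-free plasma", supplied by consenting donors.

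The Statistical analysis section says only that a three-compartment "PK model will be used to fit propofol data". It does not repeat the matrix. The blood-sampling bullet under Anaesthetic technique gives times and a maximum volume and names neither serum nor plasma.

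**The concern.** Serum and plasma are different fluids, and consecutive sentences give the same spun product both names. This is current text, with no redaction or amendment to explain it. Concentration is the dependent variable of the pharmacokinetic model, and the model is the purpose of the study, so the fluid measured is part of the definition of the data. A reader might fear being unable to label the clearance and volume estimates or compare them with other propofol models.

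The second worry is calibration. If patient samples are serum, the blanks are in a different fluid. If the standards were made up in that same plasma, any difference in recovery between the two fluids that the method did not correct would enter every measured concentration. With the dose known, concentrations that are too high or too low by a fixed proportion would move clearance and volumes by the same proportion in the opposite direction.

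**Working it through.** No figure in the plan needs reproducing here: the section gives no recovery, precision or calibration range. The check is to set the statements side by side and ask what each one describes.

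| Place in the assay section | Word used | What it describes |
|---|---|---|
| Heading | serum | patient samples |
| First sentence | plasma | patient samples |
| Collection: tube | serum | patient samples |
| Collection: product of centrifugation | plasma | patient samples |
| Storage | serum | patient samples |
| Extraction aliquot | serum | patient samples |
| Blanks | plasma | donor material |
| Donors' consent | plasma | donor material |

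**Count.** Over the whole section, serum occurs 4 times and plasma 4 times. Two of the plasma mentions concern donors' material, which can be plasma without contradicting a serum sample from a patient. For the patients' samples the split is serum 4, plasma 4 − 2 = 2. The even total suggests a stalemate that is not there.

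**Which statements direct the work.** The instructions a technician acts on are the tube to fill, what to freeze and what to pipette. All three say serum. The two plasma mentions about patients are an introductory sentence and a clause giving the purpose of centrifugation. Neither alters a step. Someone carrying out the section as written would draw blood into serum tubes, freeze serum and extract 0.5 mL of serum.

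**Calibration standards.** Their matrix is indeed not stated. The sentence on pure compounds does not help either way: it concerns identification by retention time, which is qualitative, and does not describe the calibration. The extraction sentence does put the standards through the same thymol and water step as the patient samples. Plasma blanks may suggest plasma standards, but the text does not say so.

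**Size.** A shift in the parameters needs three things: standards in a different fluid from the samples, a difference in recovery between the fluids, and no correction by the method. The documents establish none of the three and give no number for the second. The assay section sets out one procedure, and the note on orthopaedic patients varies only the nerve block, the opioid and the airway. A constant proportional error, if there were one, would therefore be common to all patients and would leave ratios between patients, and proportional covariate effects, unchanged. Absolute clearance and volumes would move, by an amount the documents do not allow anyone to state.

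**The case for a change.** The strongest case for a change is that the contradiction can be read directly from the text, that it concerns the input to the only model the plan describes, and that mending it costs a few words. Reading the samples as serum does not settle everything: the blanks are still plasma, the standards still have no stated matrix, and no equivalence check is described. If the fluids differ and no such check exists, some laboratory work might be needed, and the documents do not show how much.

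Much of this stands as description. The wording is inconsistent, the calibrator matrix is missing, and a paper reporting this study should name the fluid measured and the fluid used for standards and blanks. What does not stand is the step from there to a fault in the plan. The patient matrix can be inferred from the operative sentences. The matrix of the standards is a detail that a laboratory settles when it sets up and validates its method, and its absence from a short protocol is not evidence that it was settled badly. Nothing in the documents points to a mismatch that affected a concentration.

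**Conclusion.** The wording slip is real, but no change to the plan follows. For patient samples the text favours serum by four mentions to two, and by all three bench instructions. The unstated matrix of the standards is a gap that the analysing laboratory would fill in the ordinary course of its work. No bias is shown and no percentage can be attached to one. Correcting the words would leave the samples, the model and the estimates as they are.

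This rests on two assumptions: that the laboratory followed the tube, storage and extraction sentences as written, and that it made up its standards in a suitable matrix or had reason to treat serum and plasma as equivalent. The documents neither confirm nor contradict the second. If it failed, the consequence would be a common rescaling of absolute clearance and volumes for a constant proportional error, of a size that cannot be derived from this text.
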